1 Prevalence of HPV infection using self-sampling screening and
2 monitoring the Earlier Impact of HPV-Vaccination Program in
3 Switzerland
4
5

6 Study protocol – version 5

7 08 june 2016
8

- 9
10
11
- 12 • **Principal Investigator:** Pr [name], University Hospitals of Geneva,
13 Head of Gynecologic Division, [name], [contact]

14
15 ❖ **Co- investigators:**
16

17 [name], Msc, MPH, PhD cand. Institute of Global Health, Department of Health and
18 Community Medicine, University of Geneva and University of Applied Sciences Western
19 Switzerland, Geneva, Switzerland **Mail :** [contact]
20

21 [name], MD, Geneva Foundation for Medical Education and Research,
22 [contact]

23 [name] MD, University Hospitals of Geneva, Head of Gynecologic Division, CH-
24 [name], [contact].

25 [name], University Hospitals of Geneva, Head of Gynecologic Division, CH-
26 [name], [contact]

27 Pr [name], Institute of Global Health, Department of Health and
28 Community Medicine, University of Geneva, [contact]
29

30 **Abstract**

31

32 **Background:** Currently prevalence of HPV infections for high risk strains among young
33 women in Switzerland is unknown. In addition, since 2008 a vaccination program to prevent
34 these infections has been implemented in a number of cantons, but its actual population
35 impact is currently unknown. For now, HPV screening in Switzerland is mainly performed by
36 gynecologists or during gynecological consultation at hospital. This method is certainly
37 effective, but expensive; population coverage of screening is still insufficient. A whole
38 segment of the target population does not participate in this screening especially young
39 people of foreign origin, for various reasons: economic cost, no gynecological, and for other
40 reasons.

41 Several studies raise the effectiveness and efficiency of self-sampling to increase coverage
42 of screening, and the rate of participation of non-participants. Through this study, we
43 evaluate the possibility to use self-sampling as a screening tool in a real population,
44 document the effectiveness of this vaccination on the prevalence of HPV infections and
45 assess evolution of infection and clearance of HPV virus during 5 years in a population of
46 young unvaccinated and vaccinated girls.

47

48 **Method:** During the study, each woman will perform a vaginal swab sampling by auto to

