49 research HPV. These samples will be sent to a laboratory where HPV typing is done by PCR
50 using the Anyplex™ II technology.
51 The study will focus on a sample of 400 young women. Participants must complete a
52 questionnaire containing demographic questions and their HPV immunization status.
53 Vaccination coverage expected in this population is about 50%. Depending on the state of
54 vaccination, two different groups will be vaccinated vs unvaccinated (200 women per group).
55 The cases of HPV infection are then calculated for each group and compared as a function
56 of the status of vaccination. Statistical tests will be applied McNemar's test for comparison
57 between the HPV prevalence rates between the 2 groups.

58

59 **Expected Results:** This study will allow us to confirm the possibility of using self-sampling
60 as a method of screening and monitoring of HPV infections in the general population, it will
61 also enable us to document the effectiveness of HPV vaccination by comparing prevalence
62 rate of HPV infections among a group of young girls vaccinated and not vaccine and assess
63 evolution of infection and clearance of HPV virus.

64 **Key words:** cervical cancer, self-sampling, Human papillomavirus (HPV)

65

66 1. Background

67 Human papillomavirus (HPV) vaccination to prevent cervical cancer has been introduced in
68 Switzerland in 2008. Recommendations are that young girls aged 11 to 14 are included in
69 the immunization schedule program at school and girls aged 15 to 19 are included in a
70 “catch-up program”, for a transition period, until 2012. Within school-based program, the
71 vaccine uptake has been achieved to date with a 60% course completion, but lower rate
72 (20%) has been observed in cantons having adopted an “opportunistic” vaccination strategy.
73 Monitoring public health impact is an essential component of the intervention. Since the
74 eventual cervical cancer disease reduction will be only able to be evaluated decades after
75 exposure, current monitoring activity will focus on the anticipated earlier reduction of HPV
76 vaccine-type in the population. In 2015, seven years passed since the first vaccinated
77 cohorts entered the program; “school-vaccinated” women will be of 18 years old and “catch-
78 up vaccination” will be of 32 years old. Prior introduction of the vaccine in Switzerland, the
79 only available data was from HPV testing performed with residual cervical screening sample

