108 gynecological hospital visits. This method is certainly effective, but expensive, furthermore
109 screening coverage is still insufficient (only 30 to 40 % women's don't participate at the
110 screening) in Switzerland. Also a part of our study population don't participate in screening
111 such young people of foreign origin for various reasons, no gynecological medicine,
112 economic cost etc ...

113 Several studies raise the effectiveness and efficiency (9) of the self sampling to increase
114 screening coverage (10), participation rate of nonattenders (11, 12) self-sampling has been
115 nearly as sensitive as clinician-obtained cervical samples and more sensitive than cytology
116 for the detection of cervical intraepithelial neoplasia (CIN) for lesions of high-grade CIN-II or
117 higher (CIN-II+) (13-14) .

118 Through this study we want to evaluate the possibility of using self sampling as a screening
119 tool in a real population, yet a study in Geneva showed the possibility of its use for screening
120 a population not visiting gynecological hospital visits (15), but the actual population use
121 remains to be demonstrated.

122 **2. Objectives**

123 Through this study, we evaluate the possibility to use self sampling as a screening tool in a
124 real population, document the effectiveness of this vaccination on the prevalence of HPV
125 infections and assess evolution of infection and we will assess the evolution of viral
126 infection and clearance of throughout 5 years in a population of young, unvaccinated and
127 vaccinated girls.

128

129 **Primary objective**

- 130 • Explored the feasibility of establishing a home-based Self-HPV screening strategy in
131 general population

132

133 **Secondary objective**

- 134 • To determine the HPV prevalence of vaccine-type: 19 high-risk HPV types (16, 18, 26,
135 31, 33, 35, 39, 45, 51, 52, 53, 56, 58, 59, 66, 68, 69, 73, 82) and 9 low-risk HPV types(6,

136 11, 40, 42, 43, 44, 54, 61, 70) in young women population attending High schools in
137 Geneva and Faculty of Medicine at the University of Geneva.

138 • To generate data about vaccination impact and vaccine coverage.

139

140 • To assess the infection's evolution and clearance of HPV throughout 5 years in a
141 population of young, unvaccinated and vaccinated young women

142

143

144 **3. Material and method**

145

146 ***Inclusion criteria:***

147 • Eligible women aged between 18-31 years attending of Haute Ecole de Santé –

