148 Genève and Faculty of Medicine at the University of Geneva.

149 • Understands study procedures and accepts voluntarily to participate by signing the
150 informed consent form (ICF)

151

152 ***Exclusion criteria:***

153 • History of hysterectomy or treatment on the cervix during the last 12 months.

154

155

156 **Study Design and Methods**

157

158 Setting: The study will be conducted in collaboration with the High school of health in Geneva
159 and Faculty of Medicine at the University of Geneva. The study will be proposed to 400
160 women attending these schools.

161

162 Recruitment: It will take place in the health school of health and Faculty of Medicine at the
163 University of Geneva. Trial information on the University website will be available; it will also
164 contain a phone number for helpline. Cards to check eligibility, registration and scheduling
165 will be available. The HPV self-collection kit will be directly distributed to participants at the
166 end of their courses to School of Health and University of Geneva School of Medicine

167

168 Data collection: Vaccination status, age, menopausal status, marital status, parity, tobacco
169 consumption, medical records, geographic data, consulting-date and HPV-test result.

170

171 HPV tests: The HPV self-collection kit included a dacron swab, collection tube, instructions
172 with explanatory pictures, consent forms and a participant demographic information. The

173 HPV analysis will be performed by Real-time PCR. Delay between sampling and lab
174 processing will be noted.

175

176 Technical aspect: Written informed consent will be obtained by papier. All women will
177 perform a self sampling for HPV testing using a simple swab with no medium. The results of
178 HPV testing and sociodemographic data will be archived in a database.

179

180 Statistical analysis: The expected vaccination coverage in this population is about 50%.
181 According vaccination status, 2 different groups will be formed (vaccinated vs non-
182 vaccinated). The cases of HPV infection (status HPV+) will then be calculated for each group
183 and compared according to the vaccination status. The applied statistical tests will be
184 McNemar's test for comparison.

185

186 Sample size: Sample size was obtained based on estimated prevalence of 6% of HPV 16/18
187 infection in the Swiss population aged less than 30 years. A total of 200 specimens per group

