188 would be needed to detect about an 85% reduction in HPV 16/18 prevalence (prevalence of
189 0.9% in the vaccinated population), given an 80% power and a two-sided significance level of
190 95% (based on representative data from England). We therefore estimate that a sample size
191 of 400 women (200 in each group) will be adequate for the analyses.

192

193 Follow up: Participants will receive their results by e-mail directly via our colposcopy nurse.
194 We will follow the HPV-positive participants every 6 months during 5 years to assess the
195 evolution of their HPV status and the viral clearance. In order to do this, every 6 months they
196 will receive a self-sampling HPV kit at home, which they will return by mail to the
197 HUG for analysis.

198

199

200 **4. Statement regarding the relevance and potential contribution of the project to** 201 **cancer control**

202 Data from the registries will be used to assess the HPV prevalence of the pre-vaccine era
203 and will be the basis for monitoring infection after post-vaccine introduction. This study will
204 provide important data about the prevalence of HPV infection in a young and sexually active
205 population of women and on the proportion of vaccinated and non-vaccinated young women.

206 Despite the impact of vaccine on invasive cancers is not expected until some decades after
207 its extensive implementation, as the type-specific prevalence of HPV infection is very high in

208 young sexually active populations, the effect of a successful HPV vaccination program
209 should be quickly detected by sentinel surveillance in this sub-population.

210 Monitoring the impact of the vaccination programs by detecting type-specific infection is
211 important as it is the earliest anticipated change, and failure to detect protection from
212 infection will indicate failure to prevent cancer in the subsequent decades and allow the
213 implementation of appropriate changes in cervical cancer screening strategies.

214 This surveillance is required in order to document the expected gains in cancer prevention if
215 there is appropriate population coverage. In our case, no data is available in Switzerland.
216 Such surveillance would allow further studies to determine the duration of protection, long-
217 term safety and actual impact on health-care cost consumption.

218 In this project, 400 young girls will know their statuses for HPV infection and will obtain

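### The primary objective claims feasibility in the general population, but only women attending two Geneva schools can enter, and the visible text provides no count of women offered a kit

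*Protocol*

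**What the plan says.** **Objective and expected result.** Section 2 of the protocol gives the primary objective as "Explored the feasibility of establishing a home-based Self-HPV screening strategy in" the general population. The Abstract, under Expected Results, says the study will confirm that self-sampling can be used "as a method of screening and monitoring of HPV infections in the general population, it will" also document vaccine effectiveness.

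**Who can enter.** The inclusion criteria in section 3 begin "Eligible women aged between 18-31 years attending of Haute Ecole de" Santé in Geneva and add the Faculty of Medicine. Participation is voluntary, with signed consent. Under Recruitment, the protocol says "will be available. The HPV self-collection kit will be directly distributed to participants at the" end of their courses.

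**How the other objective is scoped.** The prevalence objective, also in section 2, names its population: "11, 40, 42, 43, 44, 54, 61, 70) in young women population attending High schools in" Geneva and the Faculty of Medicine.

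**Whom the strategy is meant to reach.** The Abstract's Background says that a whole "segment of the target population does not participate in this screening especially young" people of foreign origin. Section 1 says that part of the study population itself does not take part in screening.

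**Numbers.** Under Setting: "and Faculty of Medicine at the University of Geneva. The study will be proposed to 400" women. The Abstract (Method), Sample size and section 4 use 400 as the number studied or tested, with 200 specimens per group. Section 4 also says that the study will demonstrate a potential benefit in participation.

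**The concern.** The primary objective and the population that can be enrolled do not match. A feasibility result from women training in health and medicine, recruited where they study, describes uptake among women who are likely to be better informed about HPV and easier to reach than most. The protocol motivates the study by low coverage among women who do not attend screening because of cost, because they have no gynaecologist, or for other reasons. No recruitment step is aimed at them. If the conclusion is written as the objective is worded, it will claim more than the sample can show, and on the primary objective.

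The second issue is the denominator. Participation is a proportion of the women offered a kit. If that number is not recorded during recruitment, no later analysis plan can recover it, and the statement about participation in section 4 would have nothing to rest on.

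**Working it through.** The main point is one of scope and needs no calculation. Setting the places side by side:

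| Place in the protocol | Population stated |
|---|---|
| Section 2, Primary objective | General population |
| Abstract, Expected Results | General population |
| Section 2, prevalence objective | Women attending the two Geneva schools |
| Section 3, Inclusion criteria | Women aged 18-31 attending the two Geneva schools |
| Section 3, Setting and Recruitment | The same two schools |

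1. By the inclusion criteria, the number of the planned 400 who can come from outside the two schools is 0.
2. No text narrows the primary objective in the way the prevalence objective is narrowed. Section 4 speaks of a sub-population and of selected settings, but there it concerns surveillance of vaccine impact.
3. A larger sample from the same schools would make the estimate more precise but would not change whom it describes.

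**Participation.** The natural measure is valid specimens returned ÷ women offered a kit. The Data collection paragraph lists participant characteristics, consulting date and HPV result. These are recorded for women who take part, so they supply the numerator only. Recruitment mentions cards for eligibility and registration, but the visible text does not commit to counting offers. There is also no clinic-based comparison group, so the study cannot estimate a gain in participation over clinic-based screening.

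**The figure of 400.** The inputs, from Sample size in section 3, are 6% and 0.9% HPV 16/18 prevalence and 80% power. The stated two-sided significance level of 95% is read as alpha 0.05. With pooled variance and no continuity correction, the mean proportion is (0.06 + 0.009) / 2 = 0.0345, and

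n = [1.96·√(2 × 0.0345 × 0.9655) + 0.8416·√(0.06 × 0.94 + 0.009 × 0.991)]² / (0.06 − 0.009)²
= [0.506 + 0.215]² / 0.002601 ≈ 199.9, so 200 per group.

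The plan's figure reproduces, and 2 × 200 = 400 is therefore a number of usable specimens. The Setting sentence, read literally, makes 400 the number approached. The two agree only if every woman approached takes part and every swab is valid.

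**The case against.** The strongest reply is that the wording is loose rather than a formal target population. The objective is only to explore feasibility. Section 1 contrasts this study with an earlier Geneva study of women who do not attend gynaecological visits, so general population may simply mean women not recruited through a clinic. Section 1 also says that part of the study population does not attend screening. No estimator, test or sample size rests on a general-population inference.

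Part of this stands. It would be wrong to infer that the sample contains no non-attenders, since the protocol says otherwise. But having some among the students is not the same as recruiting to represent them. And although the objective speaks of exploring, Expected Results speak of confirming, and section 4 of demonstrating.

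A reader might also infer that the home-based element is contradicted at baseline. Kits are handed out at the schools, and only the Follow up paragraph, on HPV-positive women, says that they "will receive a self-sampling HPV kit at home, which they will return by mail to the" hospital. The documents do not support a contradiction. The kit contains instructions and a collection tube, samples are sent to a laboratory, and the delay between sampling and processing is noted. All of this fits taking the kit home. The place of baseline sampling is at most a request for clarification.

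On the missing count, it is fair to say that a recruitment log is an operational matter and that the annexed flowchart is not shown. Nothing proves that offers will go uncounted. The point is that the visible text does not secure a number that cannot be recovered afterwards.

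**Conclusion.** The concern holds as a mismatch of scope. The primary objective and Expected Results claim the general population, eligibility is confined to two Geneva schools, and nothing in the protocol reconciles the two. The consequence is an unsupported conclusion on the primary objective; the data themselves remain usable for women attending these schools. A separate analysis plan could not cure this, because it cannot widen eligibility or recover an untaken count.

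The missing count of offers is a lesser point, conditional on the flowchart not already providing it.

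A reader might infer from the Setting sentence that the study is underpowered. The documents do not support that. Every other mention treats 400 as women studied or tested, and on that dominant reading the stated 80% power stands. A loss of power would need both the literal reading of one sentence and an uptake rate that the protocol does not give. It would in any case concern the vaccination comparison and not feasibility.

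**What to change.** 1. In section 2 (Primary objective) and in the Abstract (Expected Results), replace the general population with women attending these two Geneva schools, and limit the feasibility conclusion to them.
2. At recruitment, record the number of women offered a kit and the number of valid specimens returned. Report the proportion with a 95% CI. Do not claim from this sample a participation benefit over clinic-based screening. If the annexed flowchart already provides the count, refer to it in the text.
3. Add one sentence reconciling the 400 to whom the study is proposed with the 400 to be tested.

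The cost is a narrower stated scope and a simple recruitment log. Eligibility, sample size and study procedures for participants do not change.

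### The protocol uses 400 both for the women offered the study and for the specimens analysed, so on its own calculation the stated 80% power leaves no room for non-participation

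*Protocol*

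**What the plan says.** All references are to the protocol.

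- Section 3, Setting: "The study will be proposed to 400" women at the two schools. The inclusion criteria make participation voluntary, with signed consent.
- Section 3, Sample size: "Sample size was obtained based on estimated prevalence of 6% of HPV 16/18" infection, against 0.9% in the vaccinated. "A total of 200 specimens per group" is the requirement, and the conclusion is that a sample size "of 400 women (200 in each group) will be adequate for the analyses".
- Abstract, Method: the study sample is 400, and by state of "vaccination, two different groups will be vaccinated vs unvaccinated (200 women per group").
- Section 4: 400 participants are to learn their HPV status.
- Section 3, Statistical analysis: "The expected vaccination coverage in this population is about 50" per cent, and the groups are formed by vaccination status.
- Section 2: the primary objective is the feasibility of home-based self-sampling. One secondary objective is "To generate data about vaccination impact and vaccine coverage".

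The protocol gives no participation rate and no allowance for refusal, unreturned kits or invalid swabs.

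**The concern.** A sample size counted in specimens is a number to be analysed. Setting gives the same number as the women to whom the study is offered. Read literally, each refusal, unreturned kit or unusable swab takes the analysed total below 400.

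Two things depend on this. The first is the power of the only comparison for which the protocol gives a sample size. Section 4 would read a failure to detect protection from infection as a sign that later cancer prevention will fail, so a null result from an under-sized comparison could be misread. The second is the primary objective. Participation cannot be reported cleanly unless women offered a kit and women who returned a valid specimen are counted separately, and the text uses one figure for both.

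The 200/200 split adds a further condition. Vaccination status is observed rather than assigned, so the split is whatever the recruited women turn out to be.

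**Working it through.** **Inputs.** From Sample size: p1 = 0.06 (unvaccinated), p2 = 0.009 (vaccinated), so d = 0.051; power 80%; two-sided level 5% (the protocol writes a significance level of 95%, read here as 95% confidence); 200 per group. From Setting: 400 women offered the study. Participation rates and vaccinated shares other than 50% are assumptions, used to show a range.

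**Step 1: reproduce the plan's figure.** For two independent proportions with pooled variance under the null and no continuity correction, the mean proportion is p̄ = 0.0345 and

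n = [1.960·√(2p̄(1−p̄)) + 0.842·√(p1(1−p1) + p2(1−p2))]² / d²

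= [1.960 × 0.2581 + 0.842 × 0.2556]² / 0.051² = 0.5198 / 0.002601 = 199.9, rounded up to **200 per group**.

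Power at 200/200 is 80.03%; at 199/199 it is 79.8%. The stated figure is reproduced and has no slack.

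**Step 2: fewer valid specimens, even split.** Power = Φ[(d√n − 1.960 × 0.2581) / 0.2556]. For n = 180 this is Φ[(0.6842 − 0.5059) / 0.2556] = Φ(0.698) = 75.7%. The exact columns enumerate the two binomial distributions.

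| Valid specimens (share of 400) | Plan's formula | Exact, uncorrected chi-square | Exact, Fisher |
|---|---|---|---|
| 400 (100%) | 80.0% | 85.1% | 76.5% |
| 360 (90%) | 75.7% | 80.6% | 70.5% |
| 320 (80%) | 70.7% | 74.9% | 63.3% |
| 280 (70%) | 64.9% | 68.1% | 54.8% |

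**Step 3: uneven split, all 400 specimens analysed.** With nu unvaccinated, nv vaccinated and p̄ weighted by group size:

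Power = Φ{[d − 1.960·√(p̄(1−p̄)(1/nu + 1/nv))] / √(p1(1−p1)/nu + p2(1−p2)/nv)}

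For 160 vaccinated and 240 unvaccinated, p̄ = (14.4 + 1.44)/400 = 0.0396, giving Φ[(0.0510 − 0.0390) / 0.01705] = Φ(0.703) = 75.9%.

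| Vaccinated share | Power (plan's formula) |
|---|---|
| 30% | 65.9% |
| 40% | 75.9% |
| 45% | 78.5% |
| 50% | 80.0% |
| 60% | 80.8% |
| 65% | 80.3% |
| 70% | 79.0% |

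Power is at least 80% for 200 to 265 vaccinated women out of 400, that is 50% to 66%. Chance imbalance around a true 50% is minor: the vaccinated number lies between 180 and 220 with probability 96%, and power there runs from 78.5% to 80.8%.

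**Step 4: both together.** With 320 specimens, power is 65.1% at 40% vaccinated and 72.5% at 60%. At the most favourable split (228 vaccinated of 391), 391 specimens just reach 80%, which is 391/400 = 98% of the women offered the study.

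**Step 5: women to approach for 400 valid specimens.** 400/0.9 gives 445, 400/0.8 gives 500 and 400/0.7 gives 572, rounding up.

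**The case against.** **The verb in Setting may be loose.** The Abstract, Sample size and section 4 all treat 400 as the number studied. Recruitment is open, through website information and registration cards, and no closed list of 400 invitees is described. This stands as a reason to call the point an inconsistency rather than a proven recruitment cap. It does not remove the point: if 400 are to be enrolled, the Setting sentence is wrong as written and needs the same correction.

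**The loss of power depends on the test.** This also stands. By exact calculation the uncorrected chi-square test has 85.1% power at 200/200 and still 80.6% at 180/180, so a need for full participation belongs to the plan's approximation and not to every analysis. Fisher's test moves the other way, to 76.5% at 200/200. Even the favourable test falls to 74.9% at 160/160.

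**A reader might infer that 80% power needs a near-even split.** The plan's own inputs do not support that. The sensitivity is one-sided, and a vaccinated share of 60% slightly raises power.

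**A reader might take severe shortfalls from the Background.** Its 30–40% non-participation refers to existing gynaecologist-based screening in Switzerland, the barrier that self-sampling is meant to lower, and is no forecast for health and medical students handed a kit after class. Its two uptake figures ("vaccine uptake has been achieved to date with a 60% course completion, but lower rate" of 20% in cantons with an opportunistic strategy) describe types of programme. The protocol does not place Geneva in the 20% group, and it expects about 50% here.

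**A reader might infer that groups will be filled to 200 each, which would fix the coverage estimate.** No such procedure is described.

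**The comparison is secondary.** That stands and limits the weight of the point.

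**Conclusion.** The point holds as an inconsistency with a measurable consequence. The sample size needs 400 analysable specimens, and Setting offers the study to 400 women with no allowance for loss. On the plan's own formula at an even split, power is about 76%, 71% and 65% at assumed participation of 90%, 80% and 70%; by exact chi-square it is about 81%, 75% and 68%. The vaccinated share adds a risk only if vaccinated women are a minority: with all 400 analysed, power is 76% at 40% and 66% at 30%.

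These figures take 6% and 0.9% as given and treat the groups as independent, which is how the 200 per group reproduces. The documents do not show that participation will be low or that coverage will fall below half. They show that the stated 80% has no margin for either. The consequence falls on a secondary comparison and on the clarity of the feasibility denominator, so the point is worth correcting but does not undermine the study.

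**What to change.** Reconcile Setting with Sample size in one of two ways.

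1. State that 400 is the number of valid specimens to be obtained, and record every woman offered a kit separately as the denominator for feasibility. At an assumed 80% participation, about 500 women would be approached.
2. If only 400 women will be approached, keep that number and restate the power for the expected number of valid specimens, for example about 71% at an assumed 80% participation, naming the test and method used.

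In either case, reword the 200 in each group (Sample size and Abstract) as about 200 expected in each group, and add the power at a lower vaccinated share, such as 76% at 40% with 400 specimens. The first option alone does not secure 80% if vaccinated women are a minority.

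The cost is a few lines of protocol text, with either somewhat longer recruitment or a less favourable stated power for this secondary comparison.
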